13.4 Patient information and consent

All relevant information on the study will be summarized in an integrated patient information sheet and informed consent form provided by the sponsor or the study center. A sample patient information and informed consent form is provided as a document separate to this protocol.

Based on this patient information sheet, the investigator or designee will explain all relevant aspects of the study to each patient, prior to his/her entry into the study (i.e. before any examinations and procedures associated with the selection for the study are performed or any study-specific data is recorded on study-specific forms).

The investigator will also mention that written approval of the IRB/IEC has been obtained.

26 MAR 2019 Version no. 2.0 Page: 53 of 60

Each patient will be informed about the following aspects of premature withdrawal:

- Each patient has the right to withdraw from the study at any time without any disadvantage and without having to provide reasons for this decision.
- The patient's data that have been collected until the time of withdrawal will be retained and statistically analyzed in accordance with the statistical analysis plan.
- Patient-specific data on the basis of material obtained before withdrawal may be generated after withdrawal (e.g. image reading, analysis of biological specimen such as blood, urine or tissues); these data would also be retained and statistically analyzed in accordance with the statistical analysis plan. The patient has the right to object to the generation and processing of this post-withdrawal data. The patient's oral objection may be documented in the patient's source data.

Each patient will have ample time and opportunity to ask questions.

Only if the patient voluntarily agrees to sign the informed consent form and has done so, may he/she enter the study. Additionally, the investigator will personally sign and date the form. The patient / legal representative or proxy consenter will receive a copy of the signed and dated form.

The signed informed consent statement is to remain in the investigator site file or, if locally required, in the patient's note/file of the medical institution.

In the event that informed consent is obtained on the date that baseline study procedures are performed, the study record or patient's clinical record must clearly show that informed consent was obtained prior to these procedures.

The informed consent form and any other written information provided to patients will be revised whenever important new information becomes available that may be relevant to the patient's consent, or there is an amendment to the protocol that necessitates a change to the content of the patient information and / or the written informed consent form. The investigator will inform the patient of changes in a timely manner and will ask the patient to confirm his/her participation in the study by signing the revised informed consent form. Any revised written informed consent form and written information must receive the IEC/IRB's approval / favorable opinion in advance of use.

13.5 Publication policy and use of data

The sponsor has made the information regarding the study protocol publicly available on the internet at www.clinicaltrials.gov.

All data and results and all intellectual property rights in the data and results derived from the study will be the property of the sponsor who may utilize them in various ways, such as for submission to government regulatory authorities or disclosure to other investigators.

Regarding public disclosure of study results, the sponsor will fulfill its obligations according to all applicable laws and regulations. The sponsor is interested in the publication of the results of every study it performs.

26 MAR 2019 Version no. 2.0 Page: 54 of 60

The sponsor recognizes the right of the investigator to publish the results upon completion of the study. However, the investigator, whilst free to utilize study data derived from his/her center for scientific purposes, must obtain written consent of the sponsor on the intended publication manuscript before its submission. To this end, the investigator must send a draft of the publication manuscript to the sponsor within a time period specified in the contract. The sponsor will review the manuscript promptly and will discuss its content with the investigator to reach a mutually agreeable final manuscript.

13.6 Compensation for health damage of patients / insurance

The sponsor maintains clinical trial insurance coverage for this study in accordance with the laws and regulations of the country in which the study is performed.

13.7 Confidentiality

All records identifying the patient will be kept confidential and, to the extent permitted by the applicable laws and/or regulations, will not be made publicly available.

Patient names will not be supplied to the sponsor. Only the patient number will be recorded in the CRF, and if the patient name appears on any other document (e.g. pathologist report), it must be obliterated before a copy of the document is supplied to the sponsor. Study findings stored on a computer will be stored in accordance with local data protection laws. As part of the informed consent process, the patients will be informed in writing that representatives of the sponsor, IEC/IRB, or regulatory authorities may inspect their medical records to verify the information collected, and that all personal information made available for inspection will be handled in strictest confidence and in accordance with local data protection laws.

If the results of the study are published, the patient's identity will remain confidential.

The investigator will maintain a list to enable patients to be identified.

14. Reference list

Not applicable

26 MAR 2019 Version no. 2.0 Page: 55 of 60

15. Protocol amendments

15.1 Amendment 1 — 26 MAR 2019

Editorial note

In the sections on changes to the protocol text, all protocol sections affected by the respective amendment are detailed; the sequence of the sections follows the structure of the most recent previous protocol version. As applicable, changes to the protocol text are highlighted as follows:

• Editing of an existing portion: Comparative presentation of "old text" versus "new text", with "old text" referring to the most recent previous protocol version. Deletions are erossed out in the "old text". Additions are underlined in the "new text".

In general, correction of typos or omissions are not highlighted. However, throughout the protocol, the designation of the alternative hypothesis has been changed from K_0 to H_1 to align the protocol with the terminology used in the SAP and with the general standard for designation of the alternative hypothesis. It is not considered to be a protocol change but is a correction.

15.1.1 Overview of changes to the study

- Section 10.2.1.1 MRI Equipment —This section was changed to reflect changes in MRI field strength in common use and to permit either the previously specified 1.5 and the newer 3.0 field strength and to provide greater flexibility based on the study center's available MRI equipment.
- Section 10.2.1.2 Pulse sequences This section was changed to recommend that T1w spin echo/FSE acquisition should be performed in 2D mode.
- Section 10.2.1.6.1 Quantitative contrast enhancement estimation Up to 10 lesions" has to be removed because the quantitative contrast enhancement estimation algorithm will not be applied to a single lesion or up to 10 lesions, because it is a software evaluation result for a complete image.
- Section 11.4.2.4 Confidence in diagnosis This section has been modified to clarify that frequency tables for confidence responses will not be constructed for unenhanced MRI alone.
- Section 11.4.2.6 Analysis of safety variables This section was changed to remove the reference to McNemar's tests and/or related confidence intervals, reflecting a changed analysis plan.

26 MAR 2019 Version no. 2.0 Page: 56 of 60

15.1.2 Modification 1: Section 10.2.1.1 MRI equipment

The modified text is:

The procedure will be performed using either a 1.5 or a 3.0 Tesla MRI scanner that can perform the required pulse sequences (see Section 10.2.1.2) with a dedicated head coil. The manufacturer, model, software version, and field strength of the MRI device will be recorded in the eCRF. The same scanner and required pulse sequences must be used for both the gadoterate and gadobutrol enhanced MRI's.

The same field strength (either 1.5 or 3.0) must be used for both scans. Mixed field strength scans are not permitted.

In addition, T1w enhanced sequences must be performed at or near the same post-dose time point (4-10 mins) for each study drug (gadoterate and gadobutrol).

Affected sections: No other sections.

15.1.3 Modification 2: Section 10.2.1.2. Pulse Sequences

The modified text is:

The same parameter setting must be used for unenhanced T1w images and for contrast-enhanced T1w images in each patient. T1w spin echo/FSE acquisition should be performed in 2D mode. The required pulse sequences for gadobutrol and gadoterate are:

- Unenhanced (axial and sagittal image presentation for brain)
 - o T1w spin-echo/FSE images of the whole brain axial
 - o Fluid Attenuated Inversion Recovery (FLAIR) of the whole brain axial
 - o Optional: T2w spin-echo images of the whole brain sagittal or axial
- Contrast-enhanced (axial and coronal image presentation for brain)
 - o T1w spin echo/ FSE images of the whole brain
- General considerations
 - o The MR scanner should NOT be actively retuned after the unenhanced sequences

Deviations from the specified MRI procedure will be recorded in the eCRF.

Affected sections: No other sections.

15.1.4 Modification 3: Section 10.2.1.2.1 Sequence parameters for brain imaging

The modified text is:

The recommended sequence parameters for brain imaging is displayed below in Table: 10-2.

26 MAR 2019 Version no. 2.0 Page: 57 of 60

Table 10-2: Orientation parallel to the planum sphenoidale (only for axial)

	T2	SE /FSE T1	FLAIR
Plane	Sagittal or Axial	Axial or Coronal	Axial
Pulse Sequence	Spin echo/FSE	Spin echo/FSE	IR
Patient position	Supine	Supine	Supine
Coil	Head	Head	Head
Slice thick/spacing	3- 5 skip 0- 1.5	3-5 skip 0- 1.5	3- 5 skip 0- 1.5
Frequency	≥256	≥256	≥256
Phase	≥256	≥256	≥128
Nex	≥2	≥2	≥1

Affected sections: No other sections.

15.1.5 Modification 4: Section 10.2.1.6.1 Quantitative contrast enhancement estimation

The modified text is:

Quantitative contrast enhancement estimation will be performed using an exploratory Overall Contrast Enhancement Estimation Algorithm. Descriptive statistics will be presented for each study drug (gadoterate and gadobutrol). Results will be summarized by MRI modality using. Up to 10 lesions will be identified.

Affected sections: No other sections.

15.1.6 Modification 5: Section 11.4.2.4 Confidence in diagnosis

The modified text is:

Frequency tables for confidence responses (1-4) for patients will be constructed for unenhanced MRI, combined unenhanced and gadoterate-enhanced MRI, and combined unenhanced and gadobutrol-enhanced MRI. Descriptive statistics for the combined unenhanced and gadobutrol and gadoterate enhanced MRI and their difference from unenhanced MRI will be generated. Confidence intervals for the differences will be generated.

Affected sections: No other sections.

26 MAR 2019 Version no. 2.0 Page: 58 of 60

15.1.7 Modification 6: Section 11.4.2.6 Analysis of safety variables

The modified text is:

Frequencies of TEAE s will be tabulated by contrast agent and the proportions of patients exhibiting each TEAE will be displayed. Tabulations will also be made for the body system, intensity, and attribution corresponding to each TEAE. Separate tabulations will be made for serious TEAE s. McNemar's tests and/or related confidence intervals will be used to assess the significance of the differences in incidence rates between the agents.

Affected sections: No other sections.

16. Appendices

Appendix 1: Volume of Gadobutrol 0.075 mmol/kg by Body Weight

Appendix 2: Volume of Gadoterate 0.1 mmol/kg by Body Weight

26 MAR 2019 Version no. 2.0 Page: 59 of 60

Appendix 1: Volume of Gadobutrol 0.075 mmol/kg by Body Weight

Body Weight (kg)	Volume of Gadobutrol (mL)	Body Weight (kg)	Volume of Gadobutrol (mL)
45	3.4	79	5.9
46	3.5	80	6
47	3.5	81	6.1
48	3.6	82	6.2
49	3.7	83	6.2
50	3.8	84	6.3
51	3.8	85	6.4
52	3.9	86	6.5
53	4	87	6.5
54	4.1	88	6.6
55	4.1	89	6.7
56	4.2	90	6.8
57	4.3	91	6.8
58	4.4	92	6.9
59	4.4	93	7
60	4.5	94	7.1
61	4.6	95	7.1
62	4.7	96	7.2
63	4.7	97	7.3
64	4.8	98	7.4
65	4.9	99	7.4
66	5	100	7.5
67	5	101	7.6
68	5.1	102	7.7
69	5.2	103	7.7
70	5.3	104	7.8
71	5.3	105	7.9
72	5.4	106	8
73	5.5	107	8
74	5.6	108	8.1
75	5.6	109	8.2
76	5.7	110	8.3
77	5.8	115	8.6
78	5.9	120	9

26 MAR 2019 Version no. 2.0 Page: 60 of 60

Appendix 2: Volume of Gadoterate 0.1 mmol/kg by Body Weight

Body Weight (kg)	Volume of Gadoterate (mL)	Body Weight (kg)	Volume of Gadoterate (mL)
45	9.0	79	15.8
46	9.2	80	16.0
47	9.4	81	16.2
48	9.6	82	16.4
49	9.8	83	16.6
50	10.0	84	16.8
51	10.2	85	17.0
52	10.4	86	17.2
53	10.6	87	17.4
54	10.8	88	17.6
55	11.0	89	17.8
56	11.2	90	18.0
57	11.4	91	18.2
58	11.6	92	18.4
59	11.8	93	18.6
60	12.0	94	18.8
61	12.2	95	19.0
62	12.4	96	19.2
63	12.6	97	19.4
64	12.8	98	19.6
65	13.0	99	19.8
66	13.2	100	20.0
67	13.4	101	20.2
68	13.6	102	20.4
69	13.8	103	20.6
70	14.0	104	20.8
71	14.2	105	21.0
72	14.4	106	21.2
73	14.6	107	21.4
74	14.8	108	21.6
75	15.0	109	21.8
76	15.2	110	22.0
77	15.4	115	23.0
78	15.6	120	24.0

Post-hoc examination of the Average Reader mean scores for combined (unenhanced/enhanced) gadobutrol and combined gadoterate results revealed that there was less than a 1% difference for each primary efficacy parameter. This provided a compelling reason to investigate the equivalence of the performance of combined gadobutrol and combined gadoterate. A direct comparison of the complete studies (combined image sets) is consistent with clinical practice.

Supplementary Analyses of efficacy data will be performed in the Full analysis set (FAS).

A comparison of the two combined image sets will be performed. The means, medians and standard deviations will be presented for each Blinded Reader (BR) and the Average Reader.

For each primary visualization parameter, a difference of the two combined image sets will be calculated from the values already calculated in the primary analysis as described in SAP v3.0

Means, medians, standard deviations along with the 95% two-sided CIs and one-sided p-values for the difference of the combined gadobutrol minus k* times the combined gadoterate will be presented (k represents a constant for each hypothesis).

For each primary visualization parameter, an equivalence test will be considered, where the comparison will relate to a reasonable portion (5% margin) of the difference between the combined results of gadoterate and gadobutrol. The goal is to show that performance of combined gadobutrol and combined gadoterate is equivalent regarding the three visualization parameters.

Equivalence tests at level α =0.025 will be calculated using the two one-sided t-tests (TOST) procedure, see Schuirmann (1987).

The null hypotheses for equivalence are:

• H_{01} : (gadobutrol-gadoterate) \leq -0.05* (gadoterate)

and

• H_{02} : (gadobutrol – gadoterate) $\geq +0.05^*$ (gadoterate).

The alternative hypotheses, representing equivalence, are:

• H_{11} : (gadobutrol-gadoterate) > -0.05* (gadoterate)

and

• H_{12} : (gadobutrol – gadoterate) < +0.05* (gadoterate).

Statistical significance would be achieved if both null hypotheses could be rejected with p-values ≤ 0.025 for each primary efficacy variable. In each case, the overall p-value will be calculated as the maximum of the one-sided p-values of null hypotheses H₀₁ and H₀₂, respectively.

- 2. Shells
- 2.1 Table shells

Page: 5 of 7

Reader	Treatment	Image set	Subjects	Mean	Median	SD	Min	May	95% CI Lower	95% CI Upper	one - sided p-value	p-value
1	Gadoterate 0.1 mmol/kg bw	Combined unenhanced/enhanced	XXX	XXX	XXX	XXX	XXX	XXX	Linin	Linit		
	Gadobutrol 0.075 mmol/kg bw	Combined unenhanced/enhanced	xxx	xxx	XXX	XXX	XXX	xxx				
		Difference (gadobutrol -0.95 gadoterate)	XXX	XXX	XXX	XXX	xxx	xxx	xxx	XXX	xxx	
		Difference (gadobutrol -1.05 gadoterate)	XXX	XXX	XXX	xxx	xxx	xxx	XXX	XXX	xxx	
		Equivalence Test Result										XXX
2	Gadoterate 0.1 mmol/kg bw	Combined unenhanced/enhanced	XXX	xxx	XXX	XXX	xxx	XXX				
	Gadobutrol 0.075 mmol/kg bw	Combined unenhanced/enhanced	XXX	xxx	XXX	xxx	xxx	XXX				
		Difference (gadobutrol -0.95 gadoterate)	XXX	xxx	XXX	xxx	xxx	xxx	XXX	XXX	XXX	
		Difference (gadobutrol -1.05 gadoterate)	XXX	XXX	XXX	xxx	xxx	xxx	XXX	XXX	XXX	
		Equivalence Test Result										XXX
3	Gadoterate 0.1 mmol/kg bw	Combined unenhanced/enhanced	XXX	xxx	XXX	xxx	XXX	XXX				
	Gadobutrol 0.075 mmol/kg bw	Combined unenhanced/enhanced	XXX	XXX	XXX	XXX	xxx	xxx				
		Difference (gadobutrol -0.95 gadoterate)	XXX	XXX	XXX	xxx	xxx	xxx	XXX	XXX	XXX	
		Difference (gadobutrol -1.05 gadoterate)	XXX	XXX	XXX	XXX	xxx	xxx	XXX	XXX	XXX	
		Equivalence Test Result										XXX

Table 16.4.1/11Comparison of degree of lesion contrast enhancement detected by blinded
readers for combined image sets T Equivalence Test (Full analysis set)

Page: 6 of 7

Reader	Treatment	Image set	Subjects	Mean	Median	SD	Min	Max	95% CI Lower Limit	95% CI Upper Limit	one - sided p-value	p-value
Average Reader	Gadoterate 0.1 mmol/kg bw	Combined unenhanced/enhanced	XXX	XXX	XXX	xxx	XXX	XXX				
	Gadobutrol 0.075 mmol/kg bw	Combined unenhanced/enhanced	XXX	XXX	XXX	xxx	xxx	xxx				
		Difference (gadobutrol -0.95 gadoterate)	XXX	XXX	XXX	xxx	xxx	xxx	XXX	XXX	xxx	
		Difference (gadobutrol -1.05 gadoterate)	XXX	XXX	XXX	XXX	XXX	xxx	xxx	XXX	xxx	
		Equivalence Test Result										XXX

- The 95% CI is based on a t-distribution.

- An equivalence test was calculated using the two one-sided t-tests (TOST) procedure with null hypotheses H₀₁: (gadobutrol–gadoterate) \leq -0.05* (gadoterate) and H₀₂: (gadobutrol – gadoterate) \geq +0.05* (gadoterate). The overall p-value was calculated as max(p1,p2) where p1 and p2 are the results of null hypotheses H₀₁ and H₀₂, respectively.

-The degree of lesion contrast enhancement was evaluated on an ordinal scale of 1 to 4, representing no, moderate, good and excellent enhancement respectively. The average score over lesions evaluated for each subject was used in the analysis.

- Where scans within a reader and treatment detect a different number of lesions, the zero-filled average is calculated so each average is based on the maximum number of lesions detected per reader and treatment. For the difference between treatments, the zero-filled average uses the maximum number of lesions detected per reader.

- Gadobutrol in the image set means combined unenhanced/gadobutrol enhanced image set. Gadoterate in the image set means combined unenhanced/gadoterate enhanced image set.

Table 16.4.1/12 Comparison of border delineation detected by blinded readers for combined image sets [™] Equivalence Test (Full analysis set)

Replace footnotes by:

- The 95% CI is based on a t-distribution.

- An equivalence test was calculated using the two one-sided t-tests (TOST) procedure with null hypotheses H₀₁: (gadobutrol–gadoterate) \leq -0.05* (gadoterate) and H₀₂: (gadobutrol–gadoterate) \geq +0.05* (gadoterate). The overall p-value was calculated as max(p1,p2) where p1 and p2 are the results of null hypotheses H₀₁ and H₀₂, respectively.

-The border delineation was evaluated on an ordinal scale of 1 to 4, representing none, moderate, good and excellent border delineation respectively. The average score over lesions evaluated for each subject was used in the analysis.

-Where scans within a reader and treatment detect a different number of lesions, the zero-filled average is calculated so each average is based on the maximum number of lesions detected per reader and treatment. For the difference between treatments, the zero-filled average uses the maximum number of lesions detected per reader.

- Gadobutrol in the image set means combined unenhanced/gadobutrol enhanced image set. Gadoterate in the image set means combined unenhanced/gadoterate enhanced image set.

Table 16.4.1/13 Comparison of internal morphology detected by blinded readers for combined image sets [™] Equivalence Test (Full analysis set)

Replace footnotes by:

- The 95% CI is based on a t-distribution.

- An equivalence test was calculated using the two one-sided t-tests (TOST) procedure with null hypotheses H₀₁: (gadobutrol– gadoterate) $\leq 0.05^*$ (gadoterate) and H₀₂: (gadobutrol – gadoterate) $\geq +0.05^*$ (gadoterate). The overall p-value was calculated as max(p1,p2) where p1 and p2 are the results of null hypotheses H₀₁ and H₀₂, respectively.

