3.2 Determination of Sample Size

The determination of the sample size was based on the primary noninferiority test for comparing the difference between unenhanced means and combined unenhanced/gadobutrol-enhanced means with the difference between unenhanced means and combined unenhanced/gadoterate-enhanced means.

It considers all three primary efficacy visualization parameters:

- 1. The contrast enhancement
- 2. The border delineation
- 3. The internal morphology.

For each parameter, a noninferiority hypothesis was considered, where the comparison was related to a reasonable portion of the difference between gadoterate and unenhanced. The goal is to show that the loss in the visualization parameter (gadoterate vs gadobutrol) is lower than a constant times the combined gadoterate and unenhanced to unenhanced.

In the Gadovist CNS pivotal study (study 310123) submitted to and agreed by the US Food and Drug Administration for the initial approval, the fixed noninferiority margin of 0.35 for the three visualization parameters (contrast enhancement, border delineation, internal morphology) for comparison of gadobutrol and gadoteridol (ProHance) was used for the secondary objective in that study.

In this study, a modified noninferiority margin for the primary efficacy variables will be used, which is 0.2^* (gadoterate – unenhanced), separately for each variable. In the concept planning of the study, the constant c = 0.2 was considered reasonable as this means that it would be shown that the loss in image quality with gadobutrol at lower dose is less than 20% of the gain the comparator (gadoterate) achieves over unenhanced. The rationale for the choice of c = 0.2 is also based on the results derived from the pivotal study (study 310123) as seen in the following Table 3–2. The GBCAs like gadobutrol and gadoteridol behave similar in comparison to unenhanced within one parameter, but not across parameters.

	Gadobutrol - unenhanced			Gadoteridol - unenhanced		
	n	mean (std)	0.2*mean	n	mean (std)	0.2*mean
Contrast enhancement	316	1.29 (0.56)	0.26	315	1.24 (0.53)	0.25
Border delineation	316	0.60 (0.53)	0.12	315	0.56 (0.48)	0.11
Internal morphology	316	0.61 (0.42)	0.12	315	0.58 (0.41)	0.12

Table 3–2 Results for average reader derived from study 310123

Abbreviations: n = number; std = standard error.

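### The post hoc equivalence test fixes its 5% margin after a difference below 1% was seen, yet keeps a significance rule; for two of the three variables the margin can be wider than the primary one

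*SAP*

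**What the plan says.** The protocol (4.1) and SAP v3.0 (2.1) state noninferiority as the only primary objective. SAP 3.2 and 6.2.2 set the margin at 0.2 times the gadoterate gain over unenhanced, separately for each variable. SAP 3.2 explains that success would show that "the loss in image quality with gadobutrol at lower dose is less than 20% of the gain the comparator (gadoterate) achieves over unenhanced". Neither document contains an equivalence objective, a 5% margin or an alpha for equivalence.

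The SAP supplement on equivalence (the text before its section 2, Shells) starts from a post hoc look at the Average Reader means, which "revealed that there was less than a 1% difference for each primary efficacy parameter". It draws the consequence: "This provided a compelling reason to investigate the equivalence of the performance of combined gadobutrol and combined gadoterate". It adds that comparing the complete image sets directly matches clinical practice.

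The test is run on combined scores, without subtracting unenhanced, in the full analysis set. In words, "the comparison will relate to a reasonable portion (5% margin) of the difference between the combined results of gadoterate and gadobutrol". In the hypotheses, the bounds are minus and plus 0.05 times gadoterate. The decision rule reads "Statistical significance would be achieved if both null hypotheses could be rejected with p-values" at or below 0.025 for each primary variable, and the overall p-value is the larger of the two. The shell for Table 16.4.1/11, which Tables 16.4.1/12 and 16.4.1/13 follow, has rows such as "Difference (gadobutrol -0.95 gadoterate") and an equivalence p-value for each reader and for the Average Reader.

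**The concern.** A margin has force when it is fixed before anyone knows where the estimate lies. Here the estimate was known to be within 1%, and a bound of 5% was then written around it, without clinical or historical support. A significance statement from such a test invites more weight than it can bear, because a claim of equivalence sounds stronger than one of noninferiority.

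The second issue is the yardstick. The primary margin is tied to what contrast adds. The new margin is a share of the whole combined score, which includes what the reader already sees without contrast. Where contrast adds little relative to the total, 5% of the total can be a large share of the contrast benefit. Equivalence could then be declared while tolerating a larger loss than the noninferiority test allows.

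**Working it through.** **Inputs.** SAP Table 3-2 (study 310123) gives gains over unenhanced, mean (std): contrast enhancement 1.29 (0.56) for gadobutrol and 1.24 (0.53) for gadoteridol; border delineation 0.60 (0.53) and 0.56 (0.48); internal morphology 0.61 (0.42) and 0.58 (0.41). The table note calls std a standard error, but with n = 316 that would imply an SD of 0.56 × √316 = 9.95 on a 4-point scale, so the values are read as SDs. The scales end at 4, 4 and 3. The plan enrols 180 and allows for about 25% non-evaluable: 180 × 0.75 = 135. Write G for the mean combined gadoterate score and U for the mean unenhanced score. The documents give neither, so values of G below are assumptions.

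**Step 1: the plan's own margins.** 0.2 × gain gives 0.258, 0.120 and 0.122 from the gadobutrol columns and 0.248, 0.112 and 0.116 from the gadoteridol columns. Rounded, these match Table 3-2 (0.26, 0.12, 0.12; 0.25, 0.11, 0.12).

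**Step 2: which 5%.** Gadobutrol − 0.95 × gadoterate > 0 is the same as gadobutrol − gadoterate > −0.05 × gadoterate, and the 1.05 row gives the upper bound likewise. The formulas and shells therefore use 0.05 × G. Taken literally, 5% of the difference between agents, when that difference is under 1% of G, would be under 0.05 × 0.01 × G = 0.0005 × G, or 0.0015 at G = 3. The words and the formulas cannot both stand, and the formulas are what would be run.

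**Step 3: the two margins compared.** 0.05 × G > 0.2 × (G − U) exactly when the gain G − U is below G/4, so the crossover is G = 4 × gain. If the two unenhanced sets score alike on average, a loss in combined score equals a loss in gain, and both margins are in the same units.

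| Variable | Crossover G (gadobutrol gain; gadoteridol gain) | Scale maximum | Largest possible 0.05 × G | Primary margin |
|---|---|---|---|---|
| Contrast enhancement | 5.16; 4.96 | 4 | 0.20 | 0.258; 0.248 |
| Border delineation | 2.40; 2.24 | 4 | 0.20 | 0.120; 0.112 |
| Internal morphology | 2.44; 2.32 | 3 | 0.15 | 0.122; 0.116 |

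Border delineation, against a gain of 0.60:
- G = 2.0: 0.100, 17% of the gain
- G = 2.4: 0.120, 20%
- G = 3.0: 0.150, 25%
- G = 3.5: 0.175, 29%

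Internal morphology, against a gain of 0.61:
- G = 2.0: 0.100, 16%
- G = 2.75: 0.1375, 23%
- G = 3.0: 0.150, 25%

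At the crossover, U is 2.40 − 0.60 = 1.80 for border delineation and 2.44 − 0.61 = 1.83 for internal morphology. For contrast enhancement the crossover lies beyond the top of the scale, so the 5% margin is the narrower one at the planning gains.

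**Step 4: how open the outcome was.** Take the reported difference as under 1% of G. The estimate is then at least 0.04 × G from either bound, and both one-sided tests pass if SD < 0.04 × G × √n / t, where SD is that of the per-subject score.
- n = 135 (t = 1.978): G = 2 gives 0.08 × 11.62 / 1.978 = 0.47; G = 2.5 gives 0.59; G = 3 gives 0.70.
- n = 180 (t = 1.973): 0.54, 0.68 and 0.82.

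The planning SDs, which are for one agent's gain rather than for the difference between agents, run from 0.41 to 0.56. At G = 2.5 or more the test passes across that whole range. At G = 2 it passes over part of it.

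**The case against.** The strongest reply is that the supplement overstates nothing. It calls its work post hoc and supplementary, never calls it confirmatory, and leaves the primary success rule as it was. It asks a different question, about complete image sets as used in practice, so it need not borrow the primary margin. SAP 3.2 calls 0.2 reasonable for the primary variables only, and records that the pivotal study used a fixed margin of 0.35 for these same parameters as a secondary objective. The 5% margin can never exceed 0.20. Zero-filling of undetected lesions also pulls scores down, which lowers G and narrows the margin. Finally, the other SAP supplement already shows the gadobutrol − gadoterate difference with its 95% CI beside a test at 0.2 of the gain (Table 16.4/5).

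Most of this stands and limits the point. What remains is that none of it supplies a reason for 5%, and that a significance rule and an equivalence p-value still rest on a hypothesis prompted by the result. The material already planned does not label the p-value exploratory, nor does it express the difference as a percentage of the gain.

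A reader might go further and infer three things:
- **That type I error is uncontrolled.** For a margin fixed independently of the data, two one-sided tests at 0.025, with the larger p-value taken, keep their level. The fault is when the hypothesis and margin were chosen, not how the test works.
- **That the supplement offers equivalence as a tightening of the primary margin.** It never compares the two.
- **That the wider margin applies to all three variables.** It cannot for contrast enhancement at the planning gains.

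**Conclusion.** The point holds in this form. The equivalence hypothesis, the total-score scale and an unsupported 5% margin were set after a difference below 1% was known, so a p-value from the test is descriptive and should not carry a statement of significance. Over much of the plausible range the result was largely settled when the margin was written; this rests on assumed combined means and on planning SDs standing in for an SD that is not given.

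The comparison of margins is conditional. At the planning gains from study 310123, the equivalence margin is wider than the primary one above combined means of about 2.40 (border delineation) and 2.44 (internal morphology), or 2.24 and 2.32 on the gadoteridol gains. Below those values it is narrower. It does not apply to contrast enhancement, where the equivalence margin is at most 0.20 against 0.25 to 0.26. The conflict between the margin's wording and its formulas is plain from the text. The primary noninferiority analysis is untouched, so this is a cheap improvement, not a threat to the trial's main conclusion.

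**What to change.** In the equivalence supplement and its shells:
- Remove the significance rule and the overall equivalence p-value.
- Report the gadobutrol − gadoterate difference in combined scores with its 95% CI, labelled exploratory, and give it for each variable as a percentage of the gadoterate gain over unenhanced.
- Correct the sentence describing the margin so that it agrees with the hypotheses and the 0.95 and 1.05 rows.
- If a test is kept, label it exploratory and use a margin no wider than 0.2 × (gadoterate − unenhanced) for each variable.

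This costs changes to the supplement text and table shells, with no new data. The sponsor gives up a formal equivalence claim from a post hoc test.
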